	Inforn	ned Consent	Error! Bookmark not defined.
	Formu	laire de consentement éclairé	Error! Bookmark not defined.
	5.3	Data collection tools	32
	HCW (Questionnaire	32
	Immu	nisation register extraction	40
	Delive	ry register extraction	41
	Newb	orn data tool	42
	Notes	for touchpoint calls	43
	Quest	ionnaire du Prestataire de soins	Error! Bookmark not defined.
	Extrac	tion du registre de vaccination	Error! Bookmark not defined.
	Donné	es du registre d'accouchement	Error! Bookmark not defined.
	Outil o	le collecte des données sur les nouveau-nés	Error! Bookmark not defined.
	Notes	pour les appels de suivi	Error! Bookmark not defined.
	5.4	Project Timeline	44
	5.5	Budget	Error! Bookmark not defined.
	5.6	References	46

List of Abbreviations

BCG	Bacillus Calmette–Guérin vaccine
BD	Birth Dose
bOPV	Bivalent Oral Polio Vaccine
CCE	Cold Chain Equipment
CHAI	Clinton Health Access Initiative
cMYP	Comprehensive Multi-year Plan
CMA	Centre Médicalise d'Arrondissement
CNERSH	Comité National d'Éthique de la Recherche pour la Santé Humaine
COVID-19	Corona virus disease
CS	Centre de santé
DHIS	District Health Information Software
DN	Dose de naissance
EPI	Expanded Program on Immunization
HCW	Health Care workers
Нер В	Hepatitis B Virus
IRB	Institutional Review Board
NITAG	National Immunization Technical Advisory Group
OPV	Oral Polio Vaccine
PEV	Programme Elargie de vaccination
ТВ	Tuberculoses
VPO	Vaccin Polio orale

Executive Summary

In the Cameroon Expanded Program on Immunization (EPI), the birth dose vaccine for oral polio vaccine (OPV-0) and tuberculosis vaccine (BCG), are recommended with a third birth dose vaccine for hepatitis B (HepB-BD) being considered for introduction.

Although Cameroon introduced the HepB antigen as part of the Pentavalent vaccine into the immunization program in 2005, infants are currently unprotected until the first Penta shot at six weeks. Introduction of HepB-BD is a key priority for the Cameroon government through the National Cancer Strategy document as well as the Hepatitis Prevention and Treatment Guidelines. However, the timeliness of administration of Hepatitis B vaccine within 24 hours of birth is critical to ensure the highest efficacy and prevent transmission of the virus.

While coverage rates for BCG and OPV 0 are relatively high (91% and 78% respectively), these vaccines are often administered weeks or months after birth¹, not within the 24-hour timeframe recommended for Hepatitis B birth dose. Therefore, there are concerns from the Cameroon National Immunization Technical Advisory Group (NITAG) and other stakeholders on the feasibility of achieving high timely coverage of HepB-BD. The timeliness of administration of the birth dose vaccines within facilities relies on many system components including integrated processes between maternity and immunization units and healthcare worker awareness of birth dose administration guidelines.

The main aim of this pilot study is to assess the feasibility of immunizing newborns with BCG and OPVO (and eventually HepB-BD) within 24 hours of birth by integrating routine immunization into maternity and immediate newborn care in 15 facilities in Cameroon.

Further, the specific objectives of this pilot study are to:

- 1. Integrate birth dose immunizations into maternity and immediate newborn care services
- 2. Measure the change in proportion of newborn receiving birth doses BCG and OPV0 within 24 hours compared to baseline data
- 3. Measure the change in average age of babies receiving birth doses of BCG and OPV0
- 4. Assess the operational feasibility and acceptability of interventions and describe any factors (barriers and enablers) that may influence further implementation of birth dose strategies

This feasibility assessment is to provide quantitative findings of an intervention integrating immunizations into maternity and newborn care across 15 health facilities in Cameroon. Overall, in 20 weeks an intervention phase will be followed by a final assessment. The approach will utilize quantitative data from healthcare worker surveys, the birth registry and immunization registry, and maternity unit reporting forms. The study findings will be used to inform strategy on HepB-BD introduction in Cameroon as well as interventions to strengthen service delivery structures for newborns.

¹ Chiabi et al, Vaccination of infants aged 0 to 11 months at the Yaounde Gynaeco-obstetric and pediatric hospital in Cameroon: how complete and how timely?, BMC Pediatrics, 2017

1 Introduction

1.1 Background

In the Cameroon routine immunization program, two vaccines are recommended for administration as soon as possible after birth (oral polio vaccine/OPVO and tuberculosis vaccine/BCG) with a third birth dose vaccine (hepatitis B birth dose/HepB-BD) being considered for introduction. These recommendations for timely administration of the birth dose vaccines are in line with the position of the World Health Organization (WHO) on birth vaccines, as summarized below:

- **BCG:** in countries or settings with a high incidence of Tuberculosis (TB) and/or high leprosy burden, a single dose of BCG vaccine should be *given to all healthy neonates at birth*. If the BCG vaccine cannot be given at birth, it should be given at the earliest opportunity before exposure to infection².
- OPV0: in polio-endemic countries and in countries at high risk for importation and subsequent spread
 of poliovirus, WHO recommends a bOPV birth dose also called 'zero dose' followed by a primary
 series of three bOPV doses and at least one IPV dose. The bOPV zero dose of bOPV should be
 administered at birth, or as soon as possible after birth, to maximize seroconversion rates following
 subsequent doses and to induce mucosal protection before enteric pathogens may interfere with the
 immune response.³
- HepB birth dose (HepB-BD): All newborn (including low birth weight and premature newborn) should receive their first dose of Hepatitis B vaccine as soon as possible after birth, ideally within 24 hours to be effective against vertical transmission. The timeliness of HepB-BD is important because the risk of developing chronic Hepatitis B virus (HBV) infection varies inversely with age: 80-90% of infants infected during their first year of life develop chronic infections, as opposed to 30-50% of children infected before the age of 6 years and 1-5% of adults¹.

Cameroon's HepB prevalence is estimated to be 11.9%, which is nearly double the African average prevalence (6.1%) and triple the global average prevalence (3.5%)⁴. Although Cameroon introduced the HepB antigen as part of the Pentavalent vaccine into the immunization program in 2005, infants are currently unprotected until the first Penta shot at six weeks. Furthermore, vertical transmission during this period tends to be particularly common in countries with high HBV prevalence⁵. The monovalent hepatitis B vaccine that can be given at birth is inexpensive, costing between \$0.29 and \$0.42 per dose, thus making it a small investment for a major step towards eliminating HBV completely. Further, as of 2021, Gavi will start funding HepB-BD.

² WHO position paper on BCG vaccines, February 2018

³ WHO position paper on Polio vaccines, March 2016

⁴ Global Hepatitis Report, 2017 & Bigna JJ, Amougou MA, Asangbeh SL, et al Seroprevalence of hepatitis B virus infection in Cameroon: a systematic review and meta-analysis BMJ Open 2017;7:e015298. doi: 10.1136/bmjopen-2016-015298

⁵ Gentile I, Borgia G. Vertical transmission of hepatitis B virus: challenges and solutions. Int J Womens Health. 2014;6:605-611. Published 2014 Jun 10. doi:10.2147/IJWH.S51138

The Cameroon government previously expressed the desire to introduce HepB-BD and developed a draft HepB introduction plan in 2016 with budget provisions for two consecutive years. This Plan were suspended pending the decision from GAVI to fund HepB-BD introductions. However, this will be reviewed during the preparation of the National Immunization Strategy 2021-2025. Currently, HepB-BD is included as a key priority in the National Cancer Strategy document as well as the National Strategic Plan for the Control of Viral Hepatis.

Administrative and survey coverage data in Cameroon does not capture the timing of vaccination so coverage of birth dose vaccines within 24 hours is unknown. To better understand the current service delivery system and needs for birth vaccines in Cameroon, CHAI and EPI carried out a field study in 2019 with the objective to describe timeliness of current birth dose vaccines and the barriers and facilitating factors that influence timeliness and coverage. The study was approved by the Cameroon National Ethics Committee for Human Health Research (2019/03/4447/CE/CNERSH/SP).

This was a cross-sectional study of 30 selected sites with both an immunization and labor and delivery unit across three regions (Center, Far North, and West) within Cameroon, utilizing both qualitative and quantitative approaches. The findings from the study indicate that across the 30 sites, only 4% and 7% of newborn received BCG and OPV0, respectively, within 24 hours. The reported key barriers hindering timely birth dose administration included: (i)maternity units were not equipped functioning fridges, (ii) lack of awareness and insufficient demand by caregivers for birth dose vaccines (e.g. birth dose education at antenatal visits, (iii)vaccine hesitancy among caregivers mainly due to religious beliefs, myths and rumors. The key facilitators were (i) raising awareness among caregivers on the importance of birth dose vaccinations, (ii) improving access to functioning fridges in the maternity unit and (ii) addressing practices on multidose vial policies.

Attaining high timely coverage with birth dose vaccines is a common challenge among low- and middleincome countries. This challenge has been attributed to numerous barriers including, lack of integration into maternal and newborn health programs and protocols, lack of healthcare worker and caregiver knowledge, unavailability of cold chain storage, fear of vaccine wastage for multi-dose vials, high proportions of out of facility births, and difficulties of access and demand for target cohort.^{6,7,8,9} These barriers echo those identified in 2019 in Cameroon Global best practices and lessons learned from other countries suggest that successful timely administration of the birth dose vaccines relies on many system components including integrated processes between maternity and immunization units, healthcare worker awareness of birth dose administration guidelines, and demand from mothers and community.

⁶ WHO. Practices to improve coverage of the hepatitis B birth dose vaccine, January 2013.

⁷ Miyahara, R., Jasseh, M., Gomez, P., Shimakawa, Y., Greenwood, B., Keita, K., Ceesay, S., D'Alessandro, U., & Roca, A. (2016). Barriers to timely administration of birth dose vaccines in The Gambia, West Africa. *Vaccine*, *34*(29), 3335–3341. https://doi.org/10.1016/j.vaccine.2016.05.017

⁸ Gavi the Vaccine Alliance, Annex C: Hepatitis B Birth Dose Investment Case. October 2018.

⁹ Country presentations at WHO AFRO regional workshop on Hepatitis B birth dose, June 2019.

1.2 Study Aim and Objectives

The main aim of the pilot study aim is to assess the feasibility of immunizing newborns, within selected facilities, with BCG and OPV0 within 24 hours of birth by integrating routine immunization into maternity and early newborn care. In this study only the current birth vaccines (BCG and OPV) will be assessed. The findings will inform strategies for strengthening the birth platform as well as HepB-BD introduction which is envisaged in the cMYP (2016-2021).

Further, the specific objectives of this pilot study are to:

- 1. Integrate birth dose immunizations into facility-based maternity services
- 2. Measure the change in proportion of facility births receiving birth doses BCG and OPV0 within 24 hours
- 3. Measure the change in average age of all babies receiving birth doses of BCG and/or OPV0 at the facility
- 4. Assess the operational feasibility and acceptability of interventions and describe any factors (barriers and enablers) that may influence further implementation of birth dose strategies

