2.4 Study Population

The study population will include:

- All babies received in the maternity unit, or EPI unit for OPV0 and/or BCG vaccines in the 15 study facilities, during the 1-year baseline period and the intervention period;
- HCW from the 15 facilities involved in either EPI or maternity and newborn care

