Data extraction for children in the immunization register will occur by using a sampling interval to ensure children are sampled throughout the entire year. The sampling interval will be created by taking the total number of children entered into the immunization register for the previous 12 months and dividing by our required sample size (N = 30). For instance, if 90 children were entered into the register in the past 12 months, the sampling interval will be 3; if only 30 children were entered into the register in the past 12 months, the sampling interval will be 1. With the sampling interval, the data collector will count backwards from the most recent entry in the immunization register and begin gathering data. The data collector will record the name, date of birth, and record the date(s) of immunization for each of the birth vaccines in the immunization register. Using the name and date of birth, the data collector will then cross-check with the maternity registers to confirm that same child's date of birth. Records that are missing either a date of immunization or date of birth will be recorded to help determine how many children were potentially born out of the facility, or have incomplete records, but will not count towards the total desired sample size for timeliness coverage. Data collectors will continue working backwards through the registers entering data for every Xth child (according to the sampling interval) until they have successfully recorded the

date of immunization and date of birth for 30 children. If they reach the end of the year without entering complete data on 30 children, the data collector will be instructed to loop back through the year but start now on the second child registered when counting.

At end line:

The end line registry extraction will utilize the same sampling technique as baseline. The same sample size (N = 30) will be used with the sampling period being the duration of the study period.

Proportion of babies born in facilities receiving birth dose vaccines within 24 hours – Maternity registry extraction

At baseline:

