2.14 Limitations

This pilot study will have several key limitations. The sample of the study will be small and purposeful in that it will only include 15 health facilities that meet a set of pre-defined criteria (see above). Therefore, this work will not be statistically precise nor be nationally representative and the participating sites will likely not experience certain challenges pertaining to birth vaccines that are undoubtedly experienced elsewhere in Cameroon as a whole (such as sites located in conflict zones, etc.). Instead, the purpose of the sample is to assess the feasibility of integration of birth dose vaccines BCG and OPV0 in maternity and newborn care services to gather lessons and formulate recommendations for the broader routine immunization and maternal and child health programs.

Data collected from registers to determine timing of vaccine administration results is a limitation in that it requires us to have both a date of birth and date of vaccination in facility registers. Therefore, babies who were born out of the facility (either at home or in a different facility) will not contribute to the aggregated figures, the same goes for babies who were born in the health facilities but receive vaccination elsewhere. Furthermore, we cannot guarantee the accuracy of the facility records. Key barriers and factors associated with the birth dose process will be descriptive in nature.

3 COVID-19 Impacts

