E2	WHAT CONCERNS DO YOU HAVE ABOUT ADMINISTERING BCG WITHIN 24 HOURS OF BIRTH? Do not read list. Select all that apply	Adverse events following immunization A Inadequate personnel trainingB Inadequate guidance (SOPs)C Uncertainty on contraindicationsD Multiple vaccines administered togetherE No concerns		
E3	WHAT BARRIERS HAVE YOU FACED WHEN EDUCATING MOTHERS ABOUT THE BIRTH DOSE VACCINES? Do not read list. Select all that apply	Mothers think education is a waste of timeA Custom of sequestering new-bornsB Not enough time during visitsC Lack of appropriate education materials for mothersD No barriersE Other (please specify)X		
SURVEY RE	ESULT			
NO.	QUESTION	RESPONSE CODE	SKIP	
RESULT	Record the result of the survey.	Survey complete		
	Record ending time of the survey			
DATA COLLECTOR COMMENTS				
NO.	QUESTION	RESPONSE CODE	SKIP	

	Record any comments that you have about the survey,	
Comments	particularly anything that may have affected the survey	
	completion or quality of data entry or the survey	

Immunisation register extraction

Immunization register extraction

Facility ID: _____

Date: _____

Please collect data until 30 entries are complete (all dates included) using sampling interval with both date of birth AND date of administration. For sampling interval, count how many children are entered within a year of today's date. Divide this total number by 30 to get your sampling interval. For instance, if there are 300 children within the year, your sampling interval is 300/30 or 10. Therefore, you will enter every 10th child until you reach 30 children in total with both a birth date AND a date of administration.

Child number	Q1. Date of Birth	Q2. Date of OPV0	Q3. Date BCG
		administration	administration
1	A - Date of birth listed.	A – Was vaccine	A – Was vaccine
	1 = Yes, 2 = No (If no, skip	administered?	administered?
	Q1.B)	1 = Yes, 2 = No (If no, skip	1 = Yes, 2 = No (If no, skip
		Q2.B)	Q3.B)
	B - Date listed		
		B - Date listed	B - Date listed

Delivery register extraction

Facility ID: _____

Date: _____

Does the register have the dates or administration listed for birth dose vaccines: 1 = Yes, 2 = No.

Does the register have the dates or administration listed for birth date: 1 = Yes, 2 = No.

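### The population for the average-age result is not settled: Objective 3 and Section 2.4 include every baby vaccinated at the facility, Section 2.14 leaves out babies born elsewhere, and the printed register form does not record which are which.

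*Combined protocol and SAP*

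**What the plan says.** Section 1.2 words two neighbouring objectives differently. Objective 2 is to "Measure the change in proportion of facility births receiving birth doses BCG and OPV0 within 24 hours". Objective 3 is to "Measure the change in average age of all babies receiving birth doses of BCG and/or OPV0 at the facility". Section 2.4 matches the wider wording: "All babies received in the maternity unit, or EPI unit for OPV0 and/or BCG vaccines in the 15 study facilities".

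Section 2.14 states that "babies who were born out of the facility (either at home or in a different facility) will not contribute to the aggregated figures". It makes no exception for the average-age indicator.

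For that indicator, Section 2.9.1 samples from the immunization register, and "the data collector will then cross-check with the maternity registers to confirm" the child's date of birth. A record lacking a date of birth or of immunization is noted, "to help determine how many children were potentially born out of the facility" or have incomplete records, but does not count towards the 30. End line uses the same technique and the same 30 per facility.

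The immunization register form in Section 5.3 tells the collector, in its worked example, that "you will enter every 10th child until you reach 30 children in total with both a birth date AND a date of administration". Its columns are child number, date of birth, OPV0 date and BCG date. The delivery register form, which serves the 24-hour proportion, does ask whether the child was found in the other register (its Q4).

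**The concern.** An immunization register can hold both babies delivered at that facility and babies brought in from elsewhere. The texts disagree on whether the second group belongs in the average age, and the form leaves no trace of which group a child falls in. Two collectors could follow the protocol in good faith and sample different populations, and a reader of the result could not tell.

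The two groups need not respond alike. The integrated workflow is aimed at newborns delivered in the facility (Section 1.3), and Table 4 in Section 2.7.1 leaves strategies for out-of-facility births to future studies. If the share of babies born elsewhere differs between the 12-month baseline window and the study period, the average moves even if nobody is vaccinated sooner. Section 2.11 already plans to look for a COVID-19 effect on in-facility births, which is one way in which the share could shift.

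**Working it through.** **Texts side by side, for a child with both dates in the immunization register but no entry in the maternity register**

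| Place | Does the child count? |
|---|---|
| Section 1.2, Objective 3 | Yes |
| Section 2.4 | Yes |
| Section 2.9.1 | Unclear: depends on which register's date of birth is required |
| Section 5.3, immunization register form | Yes: both dates are present |
| Section 2.14 | No, if the child was born elsewhere |

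**The plan's own figures.** The documents give no average age, no share of babies born elsewhere and no target change, so no stated result can be reproduced. The only related arithmetic, the sampling-interval examples, is correct: 90/30 = 3, 30/30 = 1 and 300/30 = 10.

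**Illustration on assumed values.** Let q be the share of sampled babies born elsewhere, and let m_in and m_out be the mean ages at vaccination of facility-born babies and of the others. Then

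mean_all = (1 − q) × m_in + q × m_out.

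Assumed, not from the documents: m_in = 14 days at baseline; m_out between 21 and 35 days; q between 10% and 50%.

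1. *Gap between the two readings at one round* = q × (m_out − m_in). With q = 30% and m_out = 35: 0.30 × 21 = 6.3 days, that is 20.3 days for all babies against 14.0 for facility-born.

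2. *Change in mix alone, both groups' ages unchanged* = (q_end − q_base) × (m_out − m_in). If q falls from 30% to 10%: −0.20 × 7 = −1.4 days with m_out = 21, and −0.20 × 21 = −4.2 days with m_out = 35. If q rises from 20% to 30%: +0.7 and +2.1 days.

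3. *Difference between the readings when q is stable*: change_all = (1 − q) × change_in + q × change_out. If facility-born age falls from 14 to 5 days (change −9.0) and the other group does not change, the all-babies change is 0.9 × −9 = −8.1 days at q = 10%, −7.2 at 20%, −6.3 at 30% and −4.5 at 50%. If the other group also improves, the difference shrinks, and it vanishes when both groups change equally.

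The two readings give the same change only if q is zero, if q is stable and both groups change equally, or if the two group means are equal at each round.

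**The case against.** The strongest reply is that Section 2.9.1 already settles the matter. Immediately after the cross-check, it sets aside records with a missing date as a pointer to birth outside the facility. A missing date of birth points that way most naturally if it means no date in the maternity register. On that reading, unmatched children are noted but not counted, and Sections 2.9.1 and 2.14 agree. This is a fair reading, but not the only one: the text does not name the register, the form asks only for two dates, and Objective 3 and Section 2.4 would still say the opposite.

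Three stronger inferences are tempting, and the documents do not support them.

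- *That the two groups could never be separated afterwards.* Section 2.9.1 has collectors record the name as well as the date of birth, so a later look-up is possible until names are removed (Section 4.2). Section 2.7.2 also allows the tools to be edited after piloting. What can be said is that the printed form holds neither the name nor the match result.
- *That the intervention acts only on facility births.* The training in Section 2.7.1 includes EPI focal points, the opening of a multi-dose vial for one child, and antenatal messages. These could lower the age of babies brought from elsewhere. The step 3 figures that hold the other group fixed are therefore one end of a range.
- *That the all-babies average is a diluted estimate of the right quantity.* As worded, Objective 3 targets all babies vaccinated at the facility, and for that target their average is the correct summary. The mix still matters for interpreting a change, but facility-born babies should not simply be put in place of the stated population.

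The reply is also right that this is not the primary outcome (Section 2.10), that all analysis is descriptive (Section 2.11), and that the planned DHIS2 comparison would give some indication of a shift in facility births. That comparison does not show the mix among the sampled children.

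**Conclusion.** The point holds as an inconsistency of population together with an unrecorded look-up. Sections 1.2 and 2.4 include babies born elsewhere, Section 2.14 leaves them out, Section 2.9.1 can be read either way, and the form counts any child with both dates. Sites may therefore differ in whom they sample, and a reported change in average age may partly reflect a change in mix.

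The size cannot be found from the documents. Every figure in days above rests on assumed shares and ages and shows only the mechanism. The 24-hour proportion is not affected, because its sample starts from the birth register. As the average age is a secondary, descriptive indicator, severity is low; the reason to act is that the remedy is nearly free.

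**What to change.** 1. Add one yes/no field to the immunization register form: found in this facility's maternity register. The collector already makes this look-up.
2. Report age at BCG and age at OPV0 for all vaccinated babies, which is Objective 3 as worded, and separately for babies found and not found in the maternity register. Give the share of each group at baseline and at end line.
3. Reconcile Sections 1.2, 2.4, 2.9.1 and 2.14 on the population for this indicator, and state in Section 2.9.1 and on the form which register's date of birth is required for a record to count.

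The cost is one form field, one extra table and a few edited sentences, best made before baseline extraction. There are two drawbacks. Some sites will have fewer than 30 facility-born records per round for the separate result. And an unmatched child may reflect an incomplete maternity register rather than birth elsewhere, so that group should be labelled as not found, not as born elsewhere.
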